9.4. Physical Examination

There will be a physical examination at baseline visit to examine and assess any abnormalities that may be present, as indicated by the patient's medical history. They will include an assessment of head, heart, lung, abdomen, musculoskeletal, skin and neurological. Results (normal, abnormal or not done) from the assessment will be reported. All deviations from normal will be recorded, including those attributable to the patient's disease.

Any new or worsening finding will be reported as a new adverse event.

The number and percentage of patients with abnormal physical exams at baseline will be summarized for the safety analysis set by treatment group and overall.

9.5. Electrocardiogram

Not applicable.

9.6. Other Safety Data

Not applicable.

10. Pharmacokinetics

Pharmacokinetic parameters are not evaluated in this study.

11. Pharmacodynamics

Pharmacodynamic parameters are not evaluated in this study.

12. Interim Analysis

After all patients have completed the 12 weeks of double-blind, randomized treatment period, the database for this portion of the study will be locked, and the study will be unblinded. Comparative efficacy data will be analyzed following this database lock.

Since the unblinding will be performed after the randomized treatment period, no adjustments to the type I error is needed.

Once all patients complete the last visit post randomization (after OLE period), the final database lock will be performed, and the remaining data will be analyzed.

13. Changes in the Planned Analysis

The changes from the protocol have are listed below:

- PSG analysis set to be used for the analysis of the endpoint based on PSG measures
- OLE analysis set to be used for the exploratory endpoints listed below:
 - Change or percent change (as used in analyses of week 12 data) from baseline to week 24 for primary and secondary endpoints
 - Change or percent change (as used in analyses of week 12 data) from week 12 to week 24 for primary and secondary endpoints
- EASI90 added to the analyses of EASI score.
- Intercurrent events have been added for the primary and key secondary endpoints in order to take into consideration the patients who discontinued due to Covid-19 pandemic, not due to covid-19 pandemic and those patients taking selected prohibited medications and/or rescue medications.
- For the responder analysis on EASI, CMH method have been changed to MMRM model as the analysis first, then if the MMRM model fails to achieve convergence, the logistic regression at each visit will be used in order to add baseline value as one of the covariates. If the logistic regression model fails to achieve convergence, CMH method will be used. Change from baseline of EASI total score will be modelled with a MMRM model.
- Subgroup analysis based on Disease Duration has been removed as disease onset is not collected
- Baseline definition for daily assessments has been updated to include one patient who completed baseline assessment from -13 to -7 instead of -6 to Day 0.
- For the responder analysis on EASI, the analysis model has been changed from GENMOD to GLIMMIX.
- Added some details for retest approach of Psychomotor Vigilance Test.

15.1. Summary of Statistical Analyses

Endpoint	Analysis Set	Primary analysis	Supportive analysis	Subgroup analysis	Estimands
Primary endpoint					
Sleep Quality NRS: the percent change from baseline to week 12 (dupilumab, placebo)	mITT	MMRM, without imputation of missing values	Sensitivity analysis: Set missing to those weeks with 3 or less available sleep NRS data. No imputation will be made for the missing data. Using the same MMRM model	Yes	Yes
Secondary endpoints					
Continuous variables	mITT	Same approach as primary endpoints	No	No	Yes (for key secondary endpoints only)
Binary variables	mITT	Cochran-Mantel-Haenszel test, define missing as non-responder	No	No	No
Exploratory endpoints					
Continuous variable	mITT	Same approach as primary endpoints	No	No	No
Days missed from school or work to week 12	mITT	Negative Binomial Model	No	No	No
PVT & ANAM	mITT	Same approach as primary endpoint	No	No	No

Endpoint	Analysis Set	Primary analysis	Supportive analysis	Subgroup analysis	Estimands
Binary variables	mITT	Same approach as secondary endpoints	No	No	No
Sleep disturbances (eg, TST, WASO) and parameters associated with AD (eg, EASI, SCORAD, pruritus NRS, DLQI, EASI, skin pain NRS, and skin burn NRS, sensitivity to touch NRS)	mITT	Correlation	No	No	No
All efficacy and Patient-Report Outcome (PRO) measures: from week 12 to week 24 and from baseline to week 24: will be analyzed separately for those originally randomized to dupilumab, and those originally randomized to placebo (and switched to dupilumab during the open label extension)	mITT	Summary stats only	No	No	No

15.2. Schedule of Study Procedures

Study Procedure													
Visit (V)	Screening 1 ^g	Screening 2 ^g	Baseline V1	V2	V3	V4	V5	Primary End point Visit V6	V7	V8	End of Study/ Early discontinuation V9 ^h	UnSch Visit	Notes
Week (W)			W0	W1	W2	W4	W8	W12	W16	W20	W24		
Day (D)				D8	D15	D29	D57	D85	D113	D141	D169		
Visit window (±d)	D (-28 to -8)	D (-7 to -1)	D1	±3d	±3d	±3d	±3d	±3d	±3d	±3d	±3d		
Enrollment Screening/Baseline:													
Inclusion and exclusion criteria	X		X										
Informed consent	X												
Demography	X												
Concurrent illness	X		X										
IVRS call	X		X		X	X	X	X	X	X	X		
Study Treatment/Concomitant Medication:													
Study drug dispensation			X ^a		X ^b	X	X	X ^c	X	X			
Concomitant medications and procedures	X	X	X	X	X	X	X	X	X	X	X	X	
Efficacy:													
Physician Assessments:													

Study Procedure													
Visit (V)	Screening 1 ^g	Screening 2 ^g	Baseline V1	V2	V3	V4	V5	Primary End point Visit V6	V7	V8	End of Study/ Early discontinuation V9 ^h	UnSch Visit	Notes
Week (W)			W0	W1	W2	W4	W8	W12	W16	W20	W24		
Day (D)			D1	D8 ±3d	D15 ±3d	D29 ±3d	D57 ±3d	D85 ±3d	D113 ±3d	D141 ±3d	D169 ±3d		
Visit window (±d)	D (-28 to -8)	D (-7 to -1)											
IGA and BSA (for eligibility purpose only)	X		X										
EASI	X		X	X	X	X	X	X	X	X	X	X	
SCORAD	X		X	X	X	X	X	X	X	X	X	X	
Patient Assessments (Daily including week preceding baseline visit):													
Sleep Quality NRS ^d		X	X	X	X	X	X	X	X	X	X	X	
Sleep Diary ^d		X	X	X	X	X	X	X	X	X	X	X	
Peak pruritus NRS, Skin pain NRS, Skin sensitivity to touch, Skin burn NRS ^d		X	X	X	X	X	X	X	X	X	X	X	
Actigraphy ^d		X	X	X	X	X	X	X	X	X	X	X	
Patient Assessment (at clinic):													
PROMIS Sleep Related Impairment SF 8a			X	X	X	X	X	X	X	X	X	X	
Epworth Sleepiness Scale (ESS)			X			X		X			X	X	

Study Procedure													
Visit (V)	Screening 1 ^g	Screening 2 ^g	Baseline V1	V2	V3	V4	V5	Primary End point Visit V6	V7	V8	End of Study/ Early discontinuation v9 ^h	UnSch Visit	Notes
Week (W)			W0	W1	W2	W4	W8	W12	W16	W20	W24		
Day (D)			D1	D8	D15	D29	D57	D85	D113	D141	D169		
Visit window (±d)	D (-28 to -8)	D (-7 to -1)	D1	±3d	±3d	±3d	±3d	±3d	±3d	±3d	±3d		
POEM			X			X		X			X	X	
DLQI			X			X		X			X	X	
HADS			X			X		X			X	X	
ACQ-5, AR-VAS			X					X			X	X	
WPAI-AD			X			X	X	X			X	X	
Assess missed school/work days			X			X	X	X	X	X	X	X	
Center assisted Assessment:													
Psychomotor Vigilance Test (PVT)	X		X					X			X	X	
Neurocognitive test (Automated Neuropsychological Assessment Metrics-ANAM)	X		X					X			X	X	
Polysomnography (sub-study, select sites) ^e			X ^e					X					
Skin Photography ^f			X	X	X	X	X	X	X	X	X	X	

Study Procedure													
Visit (V)	Screen- ing 1 ^g	Screen- ing 2 ^g	Baseline V1	V2	V3	V4	V5	Primary End point Visit V6	V7	V8	End of Study/ Early discontin- uation V9 ^h	UnSch Visit	Notes
Week (W)			W0	W1	W2	W4	W8	W12	W16	W20	W24		
Day (D)				D8	D15	D29	D57	D85	D113	D141	D169		
Visit window (±d)	D (-28 to -8)	D (-7 to -1)	D1	±3d	±3d	±3d	±3d	±3d	±3d	±3d	±3d		
Sleep diary uploading			X	X	X	X	X	X	X	X	X	X	
Safety:													
Weight	X										X		
Height	X												
Vital signs	X		X	X	X	X	X	X	X	X	X	X	
Physical examination			X										
Adverse events	X	X	X	X	X	X	X	X	X	X	X	X	
Laboratory Testing:													
Urine Pregnancy Test (WOCBP only)	X		X			X	X	X	X	X	X	X	

Abbreviations: ACQ-5 = asthma control questionnaire; AR-VAS = Allergic Rhinitis-visual analog scale; BSA = body surface area; D = day; DC = discontinuation; DLQI = dermatology life quality index; EASI = eczema area and severity index; HADS = hospital anxiety and depression scale; IGA = Investigator's global assessment; NRS = numerical rating scale; POEM = patient oriented eczema measure; PROMIS = patient-reported outcomes measurement information system; SCORAD = SCORing atopic dermatitis; UnSch = Unscheduled; V = visit; WOCBP = women of childbearing potential; WPAI-AD = work productivity and activity impairment – Atopic Dermatitis version; w = week

a Loading dose dupilumab arm 600 mg (300 mg x 2 ie, 2 syringes); 2 placebo syringes for the placebo arm.

b Regular dose dupilumab arm 300 mg (1 syringe) and 1 syringe for placebo arm, for q2w injections at sites and for home injections.

c In order to protect the blind prior to this point to reduce bias in the open label period, at the beginning of open label (week 12), for loading dose, dupilumab arm will have 1 x 300 mg syringe and 1 placebo syringe; placebo arm will need to remain 2 syringes, 300 mg each; then subsequent dose will be 1 syringe of 300 mg for all patients in both arms.

d For patients who do not participate to the PSG sub-study: Patients eligible to continue, except for baseline severity criteria, will complete baseline assessments from Day -7 to Day -1 (right before Day 1); daily assessment thereafter until week 4; then only the week before a clinical visit until last study visit. For patients who participate to the PSG sub-study: same procedures as for the other patients, except that the sleep quality NRS and the peak pruritus NRS will be completed for 5 days, from Day -7 to Day -3 prior to baseline.

- e Each patient who participates in this sub-study will have a total of 3 overnight PSGs: at baseline time point, 2 (preferably) consecutive overnight PSGs to control for "first night effect" and collect baseline data, and 1 more at week 12.
- f Not mandatory, site professional will be taking the photographs with patient's consent; Site staff will take the photos of the same lesioned areas for each visit, starting from the baseline visit. Patients will be asked to sign a separate photography informed consent at Day 1.
- g If preferred by the patient and the investigator for logistical reasons, screening can be done during a single on-site visit. In that case, all procedures planned at screening 1 and screening 2 should be done during this single screening visit. Importantly, this single screening visit will have to be done at least 7 days before the baseline visit, as patients should wear the actigraph and complete the diary for 7 days before baseline.
- h V9 assessments are applied to patients who prematurely discontinue the study, complete the treatment (end of treatment), and complete the study (end of study).

15.3. Missing Efficacy Data

15.3.1. Handling of missing data and data whose interpretations have changed

The following will be applied to all efficacy endpoints:

- Patients will be encouraged to stay in the study if they discontinue the IMP, even due to Covid-19 pandemic (IcEv1 and IcEv2).
 - If discontinuation or interruption of study treatment due to Covid-19, off-treatment data will be set to missing. The assessments after patients resume treatment will be used.
 - If discontinuation or interruption of study treatment not due to Covid-19, all data collected following schedule after the treatment discontinuation will be used in the analysis.
- Taking selected prohibited medications that affect sleep (Protocol Section 6.5.1), all sleep related assessments (sleep quality NRS, SCORAD sleep VAS and total score, PROMIS sleep impairment SF8a total score, ESS, and actigraphy data) on that corresponding night will be set to missing. AD assessments will be included in the analyses.
- Taking selected prohibited medications that affect AD (Protocol Section 6.5.1), all AD assessments will be set to missing after the medication usage.
- Taking rescue medications for AD (ie. to control intolerable AD symptoms) is allowed. For the purpose of efficacy analysis, all AD assessments will be set to missing after the medication usage.
- If a patient discontinues from treatment or from the study, or is taking rescue or selected prohibited medications, the patient will be counted as a non-responder for the time points after discontinuation or rescue/prohibited medication start for all binary endpoints.

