5 STUDY POPULATION

Prospective approval of protocol deviations to recruitment and enrollment criteria, also known as protocol waivers or exemptions, is not permitted.

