- E 10. Any other medical or psychological condition (including relevant laboratory abnormalities) that in opinion of investigator may present an unreasonable risk to the study patient as a result of his/her participation in clinical trial, may make patient's participation unreliable or may interfere with study assessments. The specific justification for patients excluded under this criterion will be noted in study documents (chart notes, CRFs, etc.)
- E 11. Presence of skin conditions that may interfere with study assessments
- E 12. Contraindications or important side effects of TCS (eg, intolerance to treatment, hypersensitivity reactions, significant skin atrophy, systemic effects), as assessed by the Investigator
- E 13. At baseline, presence of any conditions listed as criteria for study drug discontinuation (see [Section 7.1](#))

Prior/concomitant therapy

- E 14. Patients taking sedative anxiolytic or hypnotic treatments other than melatonin on a regular basis within 3 months before randomization. Occasional use (ie, no more than twice a week) is allowed, except within 2 weeks before randomization
- E 15. Patients taking systemic sedative antihistamines more than 5 days a week. Note: Patients taking systemic sedative antihistamines ≤ 5 days per week must be on stable regimens for at least 1 month before randomization, and maintain the same regimen throughout the study
- E 16. Current treatment with antidepressants, lipophilic beta blockers, clonidine, opioids, theophylline, or other medications known to interfere with sleep and may confound the study assessments, as determined by the Investigator. Note: In most cases, chronic treatments administered regularly and at stable dosing should be acceptable. Investigators

should assess the degree to which an individual medication may cause changes in sleep pattern or sleep quality during the study, compared to the pre-baseline state

- E 17. Systemic cyclosporine A (CsA), systemic corticosteroids, azathioprine (AZA), methotrexate (MTX), mycophenolate mofetil (MMF), or janus kinase (JAK) inhibitors, or phototherapy within 4 weeks prior to baseline visit
- E 18. Treatment with biologics as follows:
 - Previous treatment with dupilumab
 - Any cell-depleting agents including but not limited to rituximab: within 6 months before the baseline visit, or until lymphocyte count returns to normal, whichever is longer

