 - Other biologics: within 5 half-lives (if known) or 16 weeks prior to baseline visit, whichever is longer
- E 19. Treatment with an investigational drug within 8 weeks or within 5 half-lives (if known), whichever is longer, prior to baseline
- E 20. Regular use (more than 2 visits per week) of a tanning booth/parlor within 4 weeks of the screening visit
- E 21. Planned or anticipated use of any prohibited medications and procedures (see [Section 6.5](#))
- E 22. Treatment with live (attenuated) vaccine within 12 weeks before the screening visit

Prior/concurrent clinical study experience

- E 23. Current participation in another investigational clinical study

Diagnostic assessments

- E 24. Not applicable.

Other exclusions

- E 25. Any other condition (medical, personal, familial, social, environmental, etc.) as assessed by the Investigator, that could significantly alter sleep parameters and confound study assessments
- E 26. Planned or anticipated major surgical procedure during the patient's participation in this study
- E 27. Pregnant or breast-feeding women, or were planning to become pregnant or breastfeed during the patient's participation in this study
- E 28. Women unwilling to use adequate birth control, if of reproductive potential* and sexually active. Adequate birth control is defined as agreement to consistently practice an effective

and accepted method of contraception throughout the duration of the study and for at least 12 weeks after last dose of study drug. These include hormonal contraceptives, intrauterine device, or double barrier contraception (ie, condom + diaphragm) or a male partner with documented vasectomy. Additional requirements for acceptable contraception may apply in certain countries, based on local regulations. Investigators in these countries will be notified accordingly in a protocol clarification letter

*For females, menopause is defined as at least 12 consecutive months without menses; if in question, a follicle stimulating hormone (FSH) level of ≥ 25 mU/mL must be documented. Hysterectomy, bilateral oophorectomy, or bilateral tubal ligation must be documented, as applicable; if documented, women with these conditions are not required to use additional contraception.

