6.5 CONCOMITANT THERAPY

Any medication or vaccine (including over-the-counter or prescription medicines, vitamins, and/or herbal supplements) that the participant is receiving at the time of enrollment or receives during the study must be recorded along with:

- Reason for use
- Dates of administration including start and end dates
- Dosage information including dose and frequency

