6.5.1 Prohibited Medications and procedures

Treatment with following concomitant medications is prohibited until the end of the study:

- Sedative anxiolytic or hypnotic treatments other than melatonin
- Patients taking systemic sedative antihistamines more than 5 days per week
- Lipophilic beta blockers, opioids, theophylline, clonidine, antidepressants or other medications known to interfere with sleep and AD as determined by the Investigators
- Live (attenuated) vaccine
- Immunomodulating biologics
- Investigational drugs
- High-potency and super-potent TCS, except when used for rescue
- Systemic corticosteroids or non-steroidal systemic immunosuppressive drugs (eg, CsA, AZA, MTX, MMF, JAK inhibitors, etc.), except when used for rescue

Study drug will be immediately discontinued if any of the following are used through week 24:

- Treatment with a live (attenuated) vaccine
- Treatment with immunomodulating biologics
- Treatment with an investigational drug
- Treatment with systemic corticosteroids or non-steroidal systemic immunosuppressive drugs (eg, CsA, AZA, MTX, MMF, JAK inhibitors, etc.)

Note: If a patient receives rescue treatment with systemic corticosteroids or other systemic immunosuppressive drugs (CsA, AZA, MTX, MMF, JAK inhibitors, etc.), study treatment may be resumed if deemed appropriate by the Investigator and the medical monitor, but not sooner than 5 half-lives after the last dose of systemic rescue medication.

The following procedures are prohibited during study participation:

- Phototherapy
- Tanning in a bed/booth

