This document provides the detailed statistical methodology for the analysis of data from the Sanofi Group study LPS15497. The table, listing and figure shells supporting the statistical analysis plan (SAP) can be found in a separate SAP shell document.

The analyses described herein are based on the clinical trial protocol (Amendment 2), Version 1.0, dated on 7th April 2020. Any changes or revisions to the planned analysis described in this document will be made prior to database lock.

2. Study Objectives, Endpoints and Estimands

The study objectives and corresponding endpoints are shown in the [Table 3.1.1](#).

Table 3.1.1- Objectives and endpoints

Objectives	Endpoints
Primary	

 To evaluate the effect of dupilumab on sleep quality in adult patients with moderate to severe atopic dermatitis (AD) 	
 Percentage change from baseline to week 12 in sleep quality numerical rating scale (NRS)
Secondary	

 To evaluate the effect of dupilumab on objective and subjective quantitative sleep parameters, AD-related outcomes, and the daytime 	
 Change from baseline to week 12 in sleep efficiency (SE) based on actigraphy data Change from baseline to week 12 in total sleep time (TST) based on actigraphy data Change from baseline to week 12 in wake after sleep onset (WASO) based on actigraphy data

consequences of sleep deprivation

- Change from baseline to week 12 in sleep onset latency (SOL) based on actigraphy data
- Percent change from baseline to week 12 in Pruritus NRS
- Change from baseline to week 12 in SCORing Atopic Dermatitis (SCORAD) total score
- Change from baseline to week 12 in SCORAD sleep Visual Analog Scale (VAS)
- EASI50 (reduction of Eczema Area Severity Index [EASI] score by $\geq 50\%$ from baseline) at week 12
- EASI75 (reduction of EASI score by $\geq 75\%$ from baseline) at week 12
- EASI90 (reduction of EASI score by $\geq 90\%$ from baseline) at week 12.
- Change from baseline to week 12 in Patient Oriented Eczema Measure (POEM) total score
- Change from baseline to week 12 in Dermatology Life Quality Index (DLQI) total score
- Change from baseline to week 12 in Patient-Reported Outcomes Measurement Information System (PROMIS) Sleep Related Impairment SF8a Total Score

- To continue to assess safety and tolerability of dupilumab throughout the study

- Incidence of adverse events through week 12

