Primary endpoint	Percentage change from baseline to Week 12 in sleep quality NRS	ITT	
 Discontinuation or interruption of study treatment due to Covid-19 pandemic, off-treatment data will be set as missing (hypothetical strategy). The assessments after patients resume treatment will be used. Discontinuation or interruption of study treatment not due to Covid-19 pandemic, all data collected following schedule after the treatment discontinuation will be used in the analysis (treatment policy strategy). Taking rescue medications ^b prior to Week 12: data will be set to missing values after the medication usage (hypothetical strategy) Taking prohibited medications ^b that affect sleep: All sleep related assessments (sleep NRS, SCORing subjective sleep loss scores, PROMIS sleep disturbance short form 8a individual question scores, ESS, actigraphy data) on that corresponding night will be set to missing (hypothetical strategy) Taking prohibited medications ^b that affect AD, data will be set to missing values after the medication usage (hypothetical strategy) 	A mixed effect model for repeated measures (MMRM) under the missing at random (MAR) framework will be used. The MMRM will include treatment, baseline value, randomization stratum, visits (up to week 12), treatment by visit interaction, and baseline sleep quality NRS by visit interaction terms all as fixed effects. Randomization stratum, treatment and visits will be considered as categorical parameters. No explicit imputation will be done for missing data.
Secondary objective: To evaluate the effect of dupilumab on objective and subjective quantitative sleep parameters, AD related outcomes, and daytime consequences of sleep deprivation.				

Endpoint Category (estimand)	Estimands			Population-level summary (Analysis and missing data handling)
	Endpoint(s) ^a	Population	Intercurrent event(s) handling strategy	
Secondary endpoint (treatment policy strategy/hypothetical strategy)	Change or percent change from baseline in Sleep and AD related outcomes	ITT	Same as the primary endpoint	The same MMRM with the baseline values corresponding to the outcome variables.

^a Additional key secondary endpoints are not included in this table but would be handled with a similar strategy as the endpoint type (ie continuous, binary, time-to-event) at other weeks. The key secondary endpoints are listed in [Section 8.2.23](#).

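### SAP 15.3.1 makes a patient who takes a drug that affects only sleep an EASI non-responder from then on, although the same section keeps that patient's skin assessments

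*SAP*

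**What the plan says.** **Binary endpoints.** SAP 15.3.1 separates drugs by what they affect. The bullet opening "Taking selected prohibited medications that affect sleep (Protocol Section 6.5.1), all sleep related assessments" sets the sleep assessments of the night concerned to missing and leaves AD assessments in the analyses. Two further bullets set AD assessments to missing after a prohibited drug that affects AD, or after rescue. The last bullet drops the separation. Discontinuation, rescue or any selected prohibited drug makes the patient a non-responder on every binary endpoint at the time points that follow.

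SAP 8.2.8 models EASI50, EASI75 and EASI90 as responder variables and also models percent change in EASI total score by MMRM. None of the EASI endpoints is among the eight ordered key secondary endpoints in SAP 8.2.23. Endpoints outside that list are reported at nominal level.

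**Which drugs count.** Footnote b of SAP Table 3.1.2 refers the reader to SAP 15.11. That section repeats protocol 6.5.1 and says the sponsor will supply the coded terms. The coded list is not in the documents.

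**Stable regimens.** Protocol 6.5.1 prohibits "Lipophilic beta blockers, opioids, theophylline, clonidine, antidepressants or other medications known to interfere with sleep and AD as determined by the Investigators". Exclusion criterion E 16 names the same classes but adds "Note: In most cases, chronic treatments administered regularly and at stable dosing should be acceptable". E 21 excludes "Planned or anticipated use of any prohibited medications and procedures". For a prohibited drug that affects sleep, Table 3.1.2 removes the following for the night of use: "sleep NRS, SCORing subjective sleep loss scores, PROMIS sleep disturbance short form 8a individual question scores, ESS, actigraphy data".

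**The concern.** A sleeping tablet says nothing about the skin. The sleep-drug bullet recognises this by keeping the AD assessments, but the last bullet then records skin non-response because of the tablet. The same patient and visit can enter the percent-change model with the observed EASI and the responder models as a failure. The responder rates would then partly measure hypnotic use.

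The second, conditional concern is about sleep data. Table 4.5.1 treats prohibited-drug use as an intercurrent event. A drug taken unchanged from before baseline to Week 12 is present in both the baseline and the Week 12 value, so the change between them is still usable. Removing those nights costs precision on the primary endpoint. Use that predates randomization should be balanced between arms, so loss of precision is the main harm and bias is not.

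**Working it through.** **1. One hypnotic night before the Week 1 visit, with hypnotics on the coded list and no other event**

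| Analysis | Rule in SAP 15.3.1 | Result |
|---|---|---|
| Sleep quality NRS | sleep-drug bullet | one night missing |
| EASI percent change (MMRM) | AD assessments kept | observed score at Weeks 1, 2, 4, 8, 12 |
| EASI50/75/90 | last bullet | non-responder at Weeks 1, 2, 4, 8, 12 |

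Such a patient is plausible. E 14 admits occasional hypnotic users (at most twice a week) up to two weeks before randomization, and protocol 6.5.1 then prohibits hypnotics on study.

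**2. Size for EASI.** Let p1 and p0 be the response rates on dupilumab and placebo, and s the share of users. The documents do not give s, so 2%, 5% and 10% are assumptions. If s is the same in both arms and users respond like other patients, the recorded difference is

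p1(1 − s) − p0(1 − s) = (p1 − p0)(1 − s).

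The factor is 0.98, 0.95 or 0.90. With illustrative rates of 60% and 35%, a difference of 25 points becomes 24.5, 23.75 or 22.5.

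The equal-share assumption matters, because this use begins after randomization. With shares s1 and s0 the recorded difference is p1(1 − s1) − p0(1 − s0), which is diluted only if s0/s1 is below p1/p0 (0.60/0.35 = 1.71 here). For example, s1 = 5% and s0 = 10% give 57.0 − 31.5 = 25.5 points.

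**3. Size for the conditional sleep-data point.** Inputs from protocol 9.2 and SAP 4.1 are a difference of 25, SD 44, 2:1 allocation, two-sided alpha 0.05, 150 evaluable patients, 201 enrolled and 20% dropout. Power comes from the non-central t distribution with n1 + n2 − 2 degrees of freedom and non-centrality 25 / (44 × √(1/n1 + 1/n2)).

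- Plan's figure: with 100 and 50 patients the non-centrality is 25 / (44 × 0.1732) = 3.28 and power is 90.3%. The stated 90% is reproduced.
- Worst case: a share s loses every post-baseline sleep value, so n becomes n(1 − s).

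| Evaluable n | s = 0 | 2% | 5% | 10% |
|---|---|---|---|---|
| 150 | 90.3% | 89.7% | 88.8% | 87.1% |
| 160.8 (201 × 0.80) | 92.2% | 91.6% | 90.8% | 89.3% |

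A total of 148.4 patients gives 90% power. The break-even share is 1 − 148.4/150 = 1.1% or 1 − 148.4/160.8 = 7.7%, which is about 1.6 or 12.4 patients.

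For actigraphy total sleep time (difference 30 minutes, SD 56), 167 patients give 90.1%, which reproduces the SAP. From 160.8 patients, power falls from 88.9% to 88.3%, 87.3% or 85.5% at the same shares.

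**The case against.** **On EASI.** A reader might infer that 15.3.1 contradicts itself. The documents do not support that. The last bullet is written for binary endpoints and can be read as the specific rule that overrides the general ones. Discontinuation has the same structure: data after a non-Covid discontinuation are used, yet the patient is a non-responder on binary endpoints. Counting an event as failure is also a legitimate composite strategy. What survives is narrower. For a drug that affects only sleep the trigger has no link to the skin, and the SAP gives no reason for it. The example also needs hypnotics on the unseen list. They are the first class named in both 6.5.1 and 15.11, but their inclusion remains a condition.

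**On stable regimens.** A reader might infer that the SAP deletes all sleep data of every patient accepted under the E 16 note. The documents do not show this, for four reasons.

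- The coded list may exempt stable use.
- The closing words of the 6.5.1 item leave the matter to the investigator, so a stable drug judged acceptable under E 16 may not be prohibited at all.
- On the opposite reading E 21 excludes these patients, and protocol 5 states "Prospective approval of protocol deviations to recruitment and enrollment criteria, also known as protocol waivers or exemptions, is not permitted". Hardly anyone may then be affected.
- Deletion is by night. It is total only for a drug counted as taken on every assessed night, and the SAP does not say which night a morning dose belongs to.

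All four stand, and they keep this part conditional. On the other side, where the protocol wanted a stable-regimen exception it wrote one, for sedative antihistamines in 6.5.2. A list of drug terms alone cannot tell stable use from new use.

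**On the two deletion lists.** Table 3.1.2 omits SCORAD total and 15.3.1 includes it. A reader might infer that the longer list should be used throughout. That does not follow. It would remove the second key secondary endpoint because of a component worth at most 10 of 103 points, in a bullet that otherwise keeps AD assessments.

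**Conclusion.** The EASI point holds as a minor one. As written, and if hypnotics are on the list, a single night's use yields EASI50/75/90 non-response through Week 12 for a reason unrelated to the skin, and the responder results then rest on a different basis from the EASI percent-change model. Under equal use in both arms the effect is dilution by the share of users: 2%, 5% or 10% at the assumed shares. The confirmatory tests are untouched, because these endpoints lie outside the hierarchy.

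The stable-regimen point is secondary and conditional. Unless the coded list or the investigator's determination exempts stable use, the night-level rule would remove usable sleep data from patients enrolled under the E 16 note. The number affected is unknown and may be near zero if E 21 is enforced. In the worst case with 150 evaluable patients, primary power falls from 90.3% to 87.1% at a 10% share. Neither point supports a claim of bias in the primary result.

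**What to change.** 1. **Last bullet of SAP 15.3.1.** Limit the medication part to rescue medication and prohibited drugs that affect AD. Leave the discontinuation part unchanged.
2. **Sleep-drug bullet of SAP 15.3.1 and the matching entry in Table 3.1.2.** For the E 16 classes, apply the rule only to drugs started, or changed in dose or frequency, after randomization. Keep night-level deletion for sedative anxiolytics and hypnotics.

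The cost is three short text edits and no new data. Protocol 6.5 already records "Dates of administration including start and end dates", together with dose and frequency. The SAP provides that "Any changes or revisions to the planned analysis described in this document will be made prior to database lock". The edits should be in place before the Week 12 lock, because the study is unblinded after it.
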